### 7.3. Planned Supportive and Sensitivity Statistical Analyses

#### 7.3.1. Supportive Analyses

##### 7.3.1.1. Poisson Model

A supportive analysis will be performed whereby the number of on-treatment moderate/severe exacerbations will be analyzed using a Poisson regression model with deviance over-dispersion correction. The model specification and presentation of results will be the same as that with the negative binomial regression analysis.

Supportive Statistical Analyses – Poisson Model
Endpoint(s)

 
Annual rate of on-treatment moderate/severe exacerbations comparing FF/UMEC/VI with FF/VI
 
Annual rate of on-treatment moderate/severe exacerbations comparing FF/UMEC/VI with UMEC/VI
 

Model Specification

 
Generalized linear model assuming a Poisson distribution
 
As defined in Section 7.2
 

Model Checking & Diagnostics

 
Refer to Appendix 10: Model Checking and Diagnostics for Statistical Analysis
 

Model Results Presentation

 
As defined in Section 7.2.
 
Note, only unadjusted p-values will be displayed.
 

Example SAS code

 
Poisson regression:
 

Supportive Statistical Analyses – Poisson Model
<pre>proc genmod data=dsetin;   class trtcd gender exachis smk region subjid;   model no_exac = trtcd gender exachis smk pctpredFEV region     / dist=poisson link=log offset=log_tm type3 lrci;   [note: both contrast and estimate statements will be used for the pairwise comparisons]   lsmeans trtcd /cl diff om; run;</pre>

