The annual rate of on-treatment moderate and severe exacerbations in the FF/VI treatment arm was 0.92 based on those subjects in the FF/VI arms from the FF/VI Phase IIIa program who can be classified as 'high risk' (unpublished data: studies HZC102871 and HZC102970) according to the most recent COPD guidelines [GOLD, 2013]. Based on these data, the exacerbation rate for FF/UMEC/VI in the current study is estimated to be 0.80 for purposes of sample size calculations, with the estimate for FF/VI being 12% higher (approximately 0.91) and the estimate for UMEC/VI being 15% higher (approximately 0.94). The co-primary endpoints will be controlled for multiplicity using the truncated Hochberg method [Dmitrienko, 2008]. In order to have 90% power to detect a 15% reduction in the annual rate of moderate and severe exacerbations in the FF/UMEC/VI arm compared with the UMEC/VI arm and a 12% reduction compared with the FF/VI arm, 4000 subjects will be randomized to each of the FF/UMEC/VI and FF/VI arms, along with 2000 subjects to the UMEC/VI arm. Calculations are based on a negative binomial regression and use a two-sided 1% significance level in order to satisfy regulatory requirements of substantial evidence of efficacy for a single study. For the multiplicity hierarchy, a 2-sided 5% risk associated with incorrectly rejecting the null hypothesis (significance level) is considered acceptable for this study. The estimate of the dispersion parameter for the negative binomial model is 0.75, which is similar to that seen with fluticasone propionate/salmeterol in the TORCH study [Calverley, 2007] and the dispersion in the FF/VI exacerbation program [Dransfield, 2013].

Subjects will be randomized in a 2:2:1 proportion to the FF/UMEC/VI, FF/VI and UMEC/VI arms, respectively. All randomized subjects (approximately 10,000 in total) are considered to be evaluable for the measurement of exacerbations, irrespective of whether they permanently discontinue from IP. Assuming a 38% screen failure rate, based on the FF/VI Phase III exacerbation program, it is estimated that approximately 16,000 subjects will be screened.

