**NOTES :**

- T = Table, F = Figure, L = Listing, Y = Yes display generated.
  - Stats Analysis = Represents TFL related to any formal statistical analyses (i.e. modelling) conducted.
  - Summary = Represents TFL related to any summaries (i.e. descriptive statistics) of the observed raw data.
  - Individual = Represents FL related to any displays of individual subject observed raw data.
1. Repeat by country for the summary of exacerbation data only.
  2. Listing will include all reported exacerbations
  3. Negative binomial regression model; repeat with Poisson regression model
  4. Plot of moderate/severe adjusted exacerbation rate ratios as a separate plot for the primary analyses. Rate ratios from both the primary and all sensitivity analyses to be included as a forest plot.
  5. Box plot of annual exacerbation raw rates (see Section 11.5.3.1 for derivations of individual subject raw COPD exacerbation rate)

6. This analyses will be performed twice; once using FF/VI as the reference group and a second time using UMEC/VI as the reference group

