### 9.1.2.4. Time to Onset of Each Exacerbation

Other Efficacy Statistical Analyses
Endpoint(s)

 
• Time to onset of each on-treatment moderate/severe exacerbation
 
• Time to onset of each on-treatment severe exacerbation
 

Model Specification

 
• Andersen-Gill regression model for recurrent events
 
• Terms in the model: 
 
• Response: time to each on-treatment exacerbation (type of exacerbation dependent on endpoint)
 
• Categorical: treatment group, gender, exacerbation history (<math>\leq 1</math>, <math>\geq 2</math> moderate/severe), smoking status (screening), geographical region
 
• Continuous: post-bronchodilator % predicted FEV1 (Screening)
 
 
 
• A robust sandwich covariance matrix structure for the within subject correlation [Therneau, 2000] will be used to allow for the lack of independence among multiple events per subject over time (to achieve this, the COVS(AGGREGATE) option will be used in the PHREG statement).
 
• The ‘exact’ method will be used for handling ties. If the analysis will not run using the ‘exact’ method, then the ‘Efron’ method for handling ties will be used instead.
 

Model Checking & Diagnostics

 
• Refer to Appendix 10: Model Checking and Diagnostics for Statistical Analysis.
 

Model Results Presentation

 
• Hazard ratios and the percent reduction in risk for the pairwise treatment comparisons with associated 95% CIs and unadjusted p-values will be presented.
 

Example SAS Code
<pre>proc phreg data=dsetin covsandwich(aggregate);   id subjid;   class trtcd smk region exachis gender;   model (start stop)*eventflag(0) = trtcd smk gender exachis region pctpredFEV / risklimits   ties=exact;   hazardratio trtcd / diff=all; run;</pre>

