#### 11.12.5. Efficacy Tables

Efficacy: Tables			
No.	Popul- ation	Title	Deliverable [Priority]
COPD Exacerbations – Primary Endpoint			
2.001	ITT	Summary of On-treatment Moderate/Severe COPD Exacerbations	SAC
2.002	ITT	Summary of On-treatment Details of Moderate/Severe COPD Exacerbations	SAC
2.003	ITT	Summary of On-treatment Moderate/Severe COPD Exacerbations by Country	SAC
2.004	ITT	Analysis of On-treatment Moderate/Severe COPD Exacerbations - Negative Binomial Model (Primary Analysis of the Primary Endpoint)	SAC [1]
2.005	ITT	Analysis of On-treatment Moderate/Severe COPD Exacerbations – Poisson Model (Supportive Analysis of the Primary Endpoint)	SAC
2.006	ITT	P-values for Interactions of Treatment with Covariates for Negative Binomial Analysis of On-treatment Moderate/Severe COPD Exacerbations (Supportive Analysis of the Primary Endpoint)	SAC

Efficacy: Tables			
No.	Population	Title	Deliverable [Priority]
2.007	ITT	Analysis of Moderate/Severe COPD Exacerbations - Negative Binomial Model, Analysis Including Off-treatment Data (Sensitivity Analysis of the Primary Endpoint)	SAC
2.008	ITT	Analysis of On-treatment Moderate/Severe COPD Exacerbations - Negative Binomial Model, Imputing Data Following FF/UMEC/VI Discontinuation Using Jump to Reference Assumption (FF/VI as Reference) (Sensitivity Analysis of the Primary Endpoint)	SAC
2.009	ITT	Analysis of On-treatment Moderate/Severe COPD Exacerbations - Negative Binomial Model, Imputing Data Following FF/UMEC/VI Discontinuation Using Jump to Reference Assumption (UMEC/VI as Reference) (Sensitivity Analysis of the Primary Endpoint)	SAC
2.010	ITT	Analysis of On and Off-treatment Moderate/Severe COPD Exacerbations - Negative Binomial Model, Imputing Data Following FF/UMEC/VI Discontinuation Using Jump to Reference Assumption (FF/VI as Reference) (Sensitivity Analysis of the Primary Endpoint)	SAC
2.011	ITT	Analysis of On and Off-treatment Moderate/Severe COPD Exacerbations - Negative Binomial Model, Imputing Data Following FF/UMEC/VI Discontinuation Using Jump to Reference Assumption (UMEC/VI as Reference) (Sensitivity Analysis of the Primary Endpoint)	SAC
COPD Exacerbations – Secondary Endpoints			
2.012	ITT	Summary and Analysis of Time to First On-treatment Moderate/Severe COPD Exacerbation (Primary Analysis of Secondary Endpoint)	SAC [1]

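### The example SAS code for the supportive Poisson analysis omits the deviance over-dispersion correction that SAP 7.3.1.1 promises

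*SAP*

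**What the plan says.** The text of SAP 7.3.1.1 states that on-treatment moderate/severe exacerbations will also be analysed "using a Poisson regression model with deviance over-dispersion correction". In other respects the model and the presentation of results follow section 7.2: rate ratios with 95% intervals, here with unadjusted p-values only.

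The example code in the same section has the CLASS statement "class trtcd gender exachis smk region subjid" and the MODEL options "dist=poisson link=log offset=log_tm type3 lrci". The only addition it announces is CONTRAST and ESTIMATE statements for the pairwise comparisons.

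The result goes to Table 2.005, which section 11.12.5 labels "Poisson Model (Supportive Analysis of the Primary Endpoint".

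**The concern.** In GENMOD the over-dispersion correction has to be requested, through a scale option such as `SCALE=DEVIANCE` or `DSCALE`. Without one, the Poisson scale is held at 1 and the model-based variance equals the mean. `subjid` sits in CLASS, but no REPEATED statement uses it, so the code does not obtain a robust variance by another route.

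The text and the code therefore specify two different analyses. A programmer who follows the code would produce intervals that are too narrow and p-values that are too small, in a table meant to support the primary result. Table 2.005 could then look more precise than the negative binomial analysis only because it ignores between-subject variation that the protocol expects.

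**Working it through.** **Does anything else supply the correction?**

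- Section 7.2, from which the specification is carried over, is a negative binomial model and has no scale option.
- Appendix 10 (11.10.1.1) gives residual Q-Q plots for the Poisson model and no scale parameter.
- CONTRAST and ESTIMATE statements use whatever scale the model has. They do not set it.
- Elsewhere the SAP does carry a variance option into its code. In 9.1.2.4 the text says that "the COVS(AGGREGATE) option will be used in the PHREG statement", and the PHREG example requests the aggregated sandwich variance.

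Nothing restores the correction in 7.3.1.1.

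**Inputs for sizing (Protocol 8.2.1).** "The estimate of the dispersion parameter for the negative binomial model is 0.75", so k = 0.75. The rates are 0.80 (FF/UMEC/VI), about 0.91 (FF/VI) and about 0.94 (UMEC/VI), with 4000, 4000 and 2000 subjects. One year of exposure for everyone and no covariates are assumed. The plan gives no figure of its own on this point to reproduce.

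**Over-dispersion.** Variance/mean = 1 + kμ, which is 1 + 0.75 × 0.80 = 1.60 up to 1 + 0.75 × 0.94 = 1.705.

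**Standard error of the log rate ratio.** As coded, SE² = Σ 1/(nμ). The true value is SE² = Σ (1 + kμ)/(nμ).

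- Versus FF/VI, as coded: √(1/3200 + 1/3640) = 0.0242. True: √(1.60/3200 + 1.6825/3640) = 0.0310. Ratio 0.781.
- Versus UMEC/VI, as coded: √(1/3200 + 1/1880) = 0.0291. True: √(1.60/3200 + 1.705/1880) = 0.0375. Ratio 0.775.

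**Coverage of a nominal 95% interval.** 2Φ(1.96 × ratio) − 1 gives 87.4% versus FF/VI and 87.1% versus UMEC/VI. The expected UMEC/VI interval around 0.80/0.94 = 0.851 is 0.80 to 0.90 as coded and 0.79 to 0.92 with the true variance.

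**Error of a nominal 5% test under a common rate μ.** 2[1 − Φ(1.96/√(1 + kμ))]:

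| k | μ = 0.80 | μ = 0.91 | μ = 0.94 |
|---|---|---|---|
| 0.5 (assumed) | 9.8% | 10.4% | 10.6% |
| 0.75 (protocol) | 12.1% | 13.1% | 13.3% |
| 1.0 (assumed) | 14.4% | 15.6% | 15.9% |

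A null simulation at rate 0.80 and k = 0.75 (2000 trials) gave 11.7%.

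**With the promised deviance scale.** Expected deviance/df at k = 0.75 is 1.479, 1.574 and 1.599 for the three rates, a little below the true 1.600, 1.683 and 1.705. The test error becomes about 6% (5.1% to 6.6% over k from 0.5 to 1.0). The simulation at 0.80 gave 5.5%. Weighted over the three arms at the design rates, deviance/df = 0.4 × 1.479 + 0.4 × 1.574 + 0.2 × 1.599 = 1.541, so standard errors grow by √1.541 = 1.24, to 0.0301 and 0.0361. Coverage is then about 94% for both comparisons.

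**Shorter exposure.** If mean exposure were 0.80 year (an assumption), the uncorrected error would be 9.3% to 11.4% for rates 0.60 to 0.90.

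**The case against.** The strongest reply is that the method is specified. The text is unambiguous, the block is labelled as an example, and it contains a prose note, so it is a template and will not be run as it stands. Other examples in the SAP are as rough: the LIFETEST steps in 8.3.1 and 8.4 misspell the dataset name used by PHREG, 9.1.2.7 uses a treatment variable that is not in CLASS, and the ANCOVA code in 9.2.13.1 also lists unused CLASS variables. The documents do not show that the final program would omit the correction. This stands, and it is why the point is a text/code mismatch and not a missing method. But most of those slips would stop a program or change nothing, whereas a missing scale option runs cleanly and gives plausible output.

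A second reply is that comparing the code with the full negative binomial variance overstates the change, because the SAP promises only a deviance scale. For coverage and test error the true variance is the right standard. For the change in the printed interval the reply is right: the promised correction widens it by about 24%, not the 28% to 29% that full correction would.

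A third is that the figures are conditional. They assume full exposure and no covariates. Covariates in the model could lower the residual dispersion, but the protocol does not say whether 0.75 is already covariate-adjusted.

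Finally, the consequence is small. No decision rests on the Poisson p-values. The note to SAP Table 3 limits the forest plot: "Rate ratios from both the primary and all sensitivity analyses to be included as a forest plot", which leaves out this supportive analysis. Table 2.005 is also not among the headline displays. All of this is accepted.

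**Conclusion.** The concern holds: the example code in SAP 7.3.1.1 does not perform the correction that its text specifies, and nothing else in the SAP supplies it. If the code were followed, Table 2.005 would carry standard errors about 22% to 23% too small, 95% intervals covering about 87%, and a 12% to 13% error rate for a nominal 5% test. These figures rest on dispersion 0.75, rates of 0.80 to 0.94, a full year of exposure and no covariate adjustment. The error rate runs from about 10% to 16% over an assumed dispersion of 0.5 to 1.0. Point estimates are unchanged, and the effect stops at one supportive table. This is a minor correction that should be made so that programmers and those checking the output have one specification.

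**What to change.** In the 7.3.1.1 example, write the MODEL options as `/ dist=poisson link=log offset=log_tm scale=deviance type3 lrci`, and delete `subjid` from CLASS because nothing uses it. The stated method does not change.

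The cost is one option and one deleted variable. Compared with the code as written, the Poisson intervals become about 24% wider on the log scale at the design rates (√1.541 = 1.24). No sample size, primary result or testing rule is affected.

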**7.3.1.2. Investigation of Interactions**

The interactions between treatment and other factors (gender, exacerbation history, smoking status, region, percent predicted FEV1) will be investigated.

Supportive Statistical Analyses – Interactions
Endpoint(s)

 
• Annual rate of on-treatment moderate/severe exacerbations
 

Model Specification

 
• The interactions between treatment and other factors will be investigated as follows by adding interaction terms to the negative binomial regression model as defined in Section 7.2
 
• Separate negative binomial models will be fitted to investigate the effect of treatment by covariate interactions: (i) with the addition of an interaction term for treatment by gender; (ii) with the addition of an interaction term for treatment by exacerbation history; (iii) with the addition of an interaction term for treatment by smoking status; (iv) with the addition of an interaction term for treatment by geographical region and (v) with the addition of an interaction term for treatment by post-bronchodilator percent predicted FEV1 (Screening).
 

Model Checking & Diagnostics

 
• Refer to Appendix 10: Model Checking and Diagnostics for Statistical Analysis
 

Model Results Presentation

 
• The p-value for each interaction test will be presented.
 
• If any interaction p-value is less than 0.10 further investigations will be carried out, for example running the analysis by each category of the subgroup. Interaction p-values and any output from interaction investigation will be presented.
 

**7.3.2. Sensitivity Analyses – Investigating Missing Data**

**7.3.2.1. Including both On and Off-treatment Data**

The negative binomial regression model will be rerun to include both on- and off-treatment moderate/severe exacerbations as the response variable. The analysis will include all post-randomization (on-treatment and off-treatment, see Section 11.3.3) moderate/severe exacerbations.

Supportive Statistical Analyses – Including Both On and Off-treatment Data
Endpoints

 
• Annual rate of moderate/severe exacerbations comparing FF/UMEC/VI with FF/VI
 
• Annual rate of moderate/severe exacerbations comparing FF/UMEC/VI with UMEC/VI
 

Supportive Statistical Analyses – Including Both On and Off-treatment Data
Model Specification

 
As defined in Section 7.2
 

Model Checking & Diagnostics

 
Refer to Appendix 10: Model Checking and Diagnostics for Statistical Analysis
 

Model Results Presentation

 
As defined in Section 7.2
 
Note, only unadjusted p-values will be displayed.
 

### 7.3.2.2. Jump to Reference (J2R) - Using On-treatment Data

On-treatment exacerbations will be analysed in a sensitivity analysis to examine the robustness of the exacerbation analysis to departures from the implicit assumption that missing data is missing-at-random (MAR).

Subjects that have prematurely withdrawn from study treatment will have their “missing” data from the date of the end of study treatment up to their projected Week 52 date (see Section [11.5.1.4](#)) imputed and analysed.

The (unconditional) jump-to-reference (J2R) multiple imputation method is based on pattern mixture models [[Keene et al, 2014](#)], and uses two assumptions about the imputed exacerbations during the “unobserved” period: 1) exacerbations in all treatment groups during the “unobserved” period are imputed using model estimates from the ‘reference’ treatment group, 2) the imputed exacerbations are computed using the subject’s baseline characteristics (their model covariates), but this estimate is *not* conditioned on the observed data.

First the on-treatment negative binomial analysis is run so that samples of all the model parameters i.e. the estimated “betas” associated with treatment, gender, exacerbation history etc., and the estimated dispersion parameter can be taken (from their joint posterior distribution). From each sample, it is possible to construct a mean for any subjects with “missing” data. This mean together with the estimated dispersion parameter makes it possible to sample from the negative binomial distribution for the number of exacerbations “experienced” by the subject during their unobserved period.

The counts from the unobserved period are added to the counts from the observed period and the full data set will be analysed up to Week 52 for each sample. The results from the analyses of each sample are combined using Rubin’s formulae [[Rubin, 87](#)] as implemented in PROC MIANALYZE in SAS.

Jump-to-reference might be considered a worst case scenario which is likely to give a conservative estimate of treatment effect because the missing data is assumed to follow the same ‘reference pattern’ in all subjects regardless of their study treatment.

This J2R sensitivity analysis will be repeated twice, once using the FF/VI treatment group as the reference, and once using the UMEC/VI treatment group as the reference. However note that in both models, data from all treatment groups will be used in the model, but only one comparison will be presented.

Supportive Statistical Analyses – Jump to Reference
Endpoint(s)

 
Annual rate of on-treatment + imputed moderate/severe exacerbations (FF/VI as reference).
 
Annual rate of on-treatment +imputed moderate/severe exacerbations (UMEC/VI as reference)
 

Model Specification

 
Covariates defined in Section 7.2. Analysis described above.
 

Model Checking & Diagnostics

 
Refer to Appendix 10: Model Checking and Diagnostics for Statistical Analysis
 

Model Results Presentation

 
As defined in Section 7.2.
 
Note, only unadjusted p-values will be displayed.
 
Although all subjects will contribute to the models, only a comparison of FF/UMEC/VI and FF/VI will be presented for the FF/VI as reference analysis, and only a comparison of FF/UMEC/VI and UMEC/VI will be presented for the UMEC/VI as reference analysis
 

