**7.3.2.3. Jump to Reference (J2R) - Using On and Off-treatment Data**

All exacerbations (on and off-treatment) will be analysed with a J2R missing data sensitivity analysis as for on-treatment exacerbations. Here however, the unobserved period will be defined for subjects that prematurely withdraw from the study from the date of study conclusion up to the projected Week 52 date (see Section 11.5.1.4). Thus, all exacerbations observed in the study will be included in this analysis, not just on-treatment exacerbations.

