#### 11.5.1.4. Projected Week 52 Date

For those subjects who have withdrawn from the study prior to Week 52, a projected Week 52 date will be derived as follows:

Projected Week 52 Date = Date of randomisation + 52 weeks

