#### 11.5.1.5. At Risk Period for Calculation of Raw Event Rate

##### 11.5.1.5.1. All Cause Mortality

For calculations of raw event rate the 'at risk period' in years (used for the denominator) will be defined as follows:

- On-treatment at risk period:
  - For subjects that completed the study up to Week 52 the on-treatment at risk period will derived as:  
(minimum (date of end of study treatment + 7, date of death, date of study conclusion) – date of start of treatment + 1)/365.25
  - For subjects that prematurely withdrew from the study prior to Week 52 and that have a survival status reported the on-treatment at risk period will derived as:  
(minimum (date of end of study treatment + 7, date of death, date last known alive) – date of start of treatment + 1)/365.25
  - For subjects that prematurely withdrew from the study prior to Week 52 and that do not have a survival status reported the on-treatment at risk period will derived as:  
(minimum (date of end of study treatment + 7, date of death, date of study conclusion) – date of start of treatment + 1)/365.25
- On and off-treatment at risk period:
  - For subjects that did not prematurely discontinue study treatment the on and off-treatment at risk period will derived as:  
(minimum (date of end of study treatment + 7, date of death, date of study conclusion) – date of start of treatment + 1)/365.25
  - For subjects that prematurely discontinued the study treatment period and completed the study up to Week 52 the on and off-treatment at risk period will derived as:  
(Date of study conclusion – date of start of treatment + 1)/365.25
  - For subjects that prematurely discontinued the study treatment period and prematurely withdrew from the study prior to Week 52 the on and off-treatment at risk period will derived as  
(minimum(Date last known alive, Date of Death, Projected date of Week 52 (as defined in Section 11.5.1.4) + 7) – date of start of treatment + 1)/365.25
  - For subjects that prematurely withdrew from the study prior to Week 52 and that do not have a survival status reported the on and off-treatment at risk period will derived as:  
(Date of study conclusion – date of start of treatment + 1)/365.25

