#### **11.5.1.5.2. Other Data**

For calculations of raw event rate the ‘at risk period’ in years (used for the denominator) will be defined as follows:

- On-treatment at risk period:
  - (minimum (date of end of study treatment+1, date of death, date of study conclusion) – date of start of treatment + 1)/365.25
- Post-treatment at risk period:
  - if date of study conclusion > date of end of treatment as follows:  
(date of study conclusion – date of end of treatment - 1)/365.25
  - Else post-treatment at risk period will be set to 0

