**11.5.2.2. Subject Disposition**

Subject Disposition

 
• For Kaplan-Meier plots of study withdrawal over time and discontinuation from study treatment over time, censoring will be performed as follows:                             
 
○ For study withdrawal, subjects are represented from their Day 1 date to the date of early withdrawal from the study (or date of death). Subjects that completed the study are censored at the earliest of the date of completion and Day 365.
 
○ For discontinuation from study treatment, subjects are represented from their Day 1 date to the date of discontinuation from study treatment (or date of death). Subjects that complete study treatment per protocol are censored at the earliest of their study treatment stop date and Day 365.
 
 
 

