**COPD Exacerbations****Offset variable for rate of exacerbations**

For analyses of rate of moderate/severe COPD exacerbations, the offset variable will be defined as follows:

- Including on-treatment data only
  - logarithm of (on-treatment at risk period, as defined in Section 11.5.1.5.2)
- Including both on and off-treatment data
  - logarithm of ([total time in study per subject (defined in Section 11.5.4.1)]/365.25).
- Jump to reference (using on-treatment data)
  - For subjects that complete study treatment:  
logarithm of (on-treatment at risk period, as defined in Section 11.5.1.5.2)
  - For subjects that prematurely discontinue study treatment but complete the study up to Week 52:  
logarithm of ([Actual date of Week 52 – date of start of treatment + 1]/365.25)
  - For subjects that prematurely discontinue from study treatment and withdraw from the study prior to Week 52:  
logarithm of ([Projected Week 52 date (as defined in Section 11.5.1.4) – date of start of treatment + 1]/365.25)
- Jump to reference (using on and off-treatment data)
  - For subjects that complete study treatment:  
logarithm of ([total time in study per subject (defined in Section 11.5.4.1)]/365.25)
  - For subjects that prematurely discontinue study treatment but complete the study up to Week 52:  
logarithm of ([Actual date of Week 52 – date of start of treatment + 1]/365.25)
  - For subjects that prematurely discontinue from study treatment and withdraw from the study prior to Week 52:  
logarithm of ([Projected Week 52 date (as defined in Section 11.5.1.4) – date of start of treatment + 1]/365.25)

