**Time to First On-treatment Exacerbation**

- The time to first on-treatment exacerbation will be calculated as exacerbation onset date of first on-treatment exacerbation – date of start of treatment + 1.
- Subjects will be represented from their Day 1 date to the start date of their first exacerbation or date of censoring. Subjects that have not experienced an on-treatment exacerbation are censored at the earliest of the date of their treatment stop date +1 day or the date of death.

COPD Exacerbations
Time to First Exacerbation Including Off-treatment data

 
The time to first exacerbation including off-treatment data will be calculated as exacerbation onset date of first exacerbation – date of start of treatment + 1.
 
Only exacerbations reported during the on-treatment and post-treatment study phases will be considered (see Section 11.3.3 for details of assigning study phase)
 
Subjects will be represented from their Day 1 date to the start date of their first exacerbation or date of censoring. Subjects that have not experienced an on or off-treatment exacerbation are censored at the earliest of (date of study conclusion or the date of death).
 

Time to First On-treatment Moderate/severe Exacerbation or Premature Study Treatment Discontinuation

 
The time to first on-treatment moderate/severe exacerbation will be calculated as exacerbation onset date of first on-treatment moderate/severe exacerbation – date of start of treatment + 1.
 
The time to study treatment discontinuation will be calculated as the date of premature study treatment discontinuation – date of start of treatment + 1.
 
The time to first on-treatment moderate/severe exacerbation or study treatment discontinuation is defined as the earliest of the time to first on-treatment moderate/severe exacerbation or time to premature study treatment discontinuation.
 
Subjects will be represented from their Day 1 date to the earliest of the event or censoring. Subjects who do not experience the event will be censored at the earliest of the date of their treatment stop date +1 day or the date of death.
 

Time to Each On-treatment Exacerbation

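### Both jump-to-reference analyses of the primary endpoint run past death: the imputation window and offset should stop at the date of death (minor)

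*SAP*

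**What the plan says.** **Imputation window.** In SAP 7.3.2.2, subjects who stop treatment early have exacerbation counts imputed "from the date of the end of study treatment up to their projected Week 52 date". In 7.3.2.3, which keeps observed off-treatment data, the window for subjects who leave the study early runs "from the date of study conclusion up to the projected Week 52 date". Section 11.5.1.4 defines the end point: "Projected Week 52 Date = Date of randomisation + 52 weeks".

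**Offset.** For each jump-to-reference (J2R) analysis, 11.5.3.1 gives three classes: those who complete treatment, those who stop treatment but reach Week 52 in the study, and a last class, "For subjects that prematurely discontinue from study treatment and withdraw from the study prior to Week 52". For the last class the offset also runs to the projected Week 52 date. Death is not mentioned.

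**Contrast.** The primary offset uses the on-treatment at-risk period in 11.5.1.5.2, which ends at "minimum (date of end of study treatment+1, date of death, date of study conclusion". The mortality at-risk period in 11.5.1.5.1 caps the same projected date at death: "minimum(Date last known alive, Date of Death, Projected date of Week 52".

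**The other sensitivity analysis.** In the exacerbation-or-discontinuation analysis (11.5.3.1), subjects without the event "will be censored at the earliest of the date of their treatment stop date +1 day or the date of death". For the Kaplan-Meier plot of treatment discontinuation, 11.5.2.2 says "subjects are represented from their Day 1 date to the date of discontinuation from study treatment (or date of death". Under 11.5.1.3, treatment is completed only if it was not stopped early and Visit 7 was attended.

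**The concern.** The J2R analyses are prespecified checks on the missing-at-random assumption behind the primary result. They are meant to fill in exacerbations that a subject could have had but that were not recorded. A subject who has died can have none, so that time is not missing. Imputing it puts impossible events and person-time into the check and makes it treat these subjects differently from the primary analysis it is supposed to test.

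The SAP caps follow-up at death explicitly elsewhere, including for this same projected date, so a programmer following the J2R text has no reason to assume an unwritten cap.

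**Working it through.** The plan states no figure on this point, so there is none to reproduce. The check has a textual part and a numerical part.

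**1. Does the rule reach subjects who die?** Take a subject who stops treatment, is followed by telephone, and dies before Week 52. The subject discontinued early on any reading. The subject had no Visit 7 attendance or telephone contact, so did not complete the study (11.5.1.3). Sections 11.3.2 and 11.5.1.5.1 handle deaths within the class that withdrew before Week 52. The only J2R offset that fits is the last class, which runs to the projected Week 52 date.

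**2. One subject.** Suppose death is on Day 100 and treatment started on the day of randomisation.
- Time alive: 100/365.25 = 0.274 years.
- J2R offset as written: (364 + 1)/365.25 = 0.999 years.
- Time credited after death: 365 - 100 = 265 days = 0.7255 years.
- Protocol 8.2.1 planning rates: 0.80 for FF/UMEC/VI, so FF/VI = 0.80/0.88 = 0.909 and UMEC/VI = 0.80/0.85 = 0.941. These match the plan's approximate 0.91 and 0.94.
- Exacerbations imputed after death: 0.7255 x 0.909 = 0.66 (FF/VI reference) or 0.7255 x 0.941 = 0.68 (UMEC/VI reference).

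**3. One arm of 4,000.** Mortality is assumed to be 1-3%, with death mid-year on average.
- Person-years after death: 4,000 x 0.01 x 0.5 = 20, up to 4,000 x 0.03 x 0.5 = 60.
- Events imputed after death: from 20 x 0.909 = 18 to 60 x 0.941 = 57 (rounded).

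**4. Rate ratio.** Assume 20% non-fatal discontinuation, mid-year on average. Write R for the true ratio, d for the proportion dying, and D = d/2 for mean time lost to death. Observed time is T = 1 - 0.10 - D.
- As written: T x R + 0.10 + D (total time is 1).
- Stopped at death: (T x R + 0.10)/(1 - D).
- Example, R = 0.85 and d = 3%: D = 0.015 and T = 0.885. As written, 0.75225 + 0.115 = 0.8673. Stopped at death, 0.85225/0.985 = 0.8652.

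| Reference | Deaths | As written | Stopped at death | Shift |
|---|---|---|---|---|
| FF/VI (R = 0.88) | 1% | 0.8926 | 0.8921 | 0.0005 |
| | 2% | 0.8932 | 0.8921 | 0.0011 |
| | 3% | 0.8938 | 0.8922 | 0.0016 |
| UMEC/VI (R = 0.85) | 1% | 0.8658 | 0.8651 | 0.0007 |
| | 2% | 0.8665 | 0.8652 | 0.0013 |
| | 3% | 0.8673 | 0.8652 | 0.0020 |

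With 2% deaths and 10% or 30% discontinuation the shift is 0.0010-0.0014. With 18% stopping in total, deaths included, and R = 0.85, the ratio is 0.8635 as written and 0.8628-0.8614 when stopped at death. The shift is towards 1 because it comes from FF/UMEC/VI subjects being imputed at the reference rate; imputing the reference arm at its own rate leaves that arm's rate unchanged.

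**5. Against sampling error.** With dispersion 0.75 and a full year of exposure, the SE of the log ratio versus UMEC/VI is sqrt[(1/0.80 + 0.75)/4000 + (1/0.941 + 0.75)/2000] = 0.0375. The largest shift is ln(0.8673/0.8652) = 0.0024, or about 6% of one SE.

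**6. Exacerbation-or-discontinuation analysis.** Section 11.5.1.3 makes a subject who dies on treatment a non-completer. Section 11.5.2.2 names death separately from discontinuation but lets either end follow-up. Section 11.5.3.1 lists death only as a censoring date, and only for subjects without the event. Protocol 4.4.4 has no death category among its reasons for stopping treatment. Nothing says whether such a death is a premature discontinuation. In a simulation (20% per year discontinuation, dispersion 0.75, 12% reduction), counting deaths rather than censoring them moved the hazard ratio by 0.0015-0.004 with equal mortality of 1-3% per year, and by about 0.02 with 2% versus 4% per year, in a direction set by which arm had more deaths.

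**The case against.** The strongest case against acting is that this is silence, not an instruction, and that it hardly matters. No passage says deaths are to be imputed. Events and offset are extended together, so the imputed rate stays coherent. Imputing what would have happened had the subject lived is a strategy some would defend. The SAP already describes J2R as possibly a worst case and conservative, and the extra imputation errs the same way. The analysis shows only unadjusted p-values and lies outside the testing hierarchy. Section 7.3.2.1 adds a sensitivity analysis with no imputation at all.

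The point about size stands in full. The point about intent does not: the SAP neither states nor justifies imputing beyond death, calls the period missing data, and caps the same projected date at death for mortality. For a subject who stops treatment and dies later, the written rule leads past death.

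A reader might also infer that the exacerbation-or-discontinuation analysis censors on-treatment deaths as event-free. The documents do not support that. Fatal exacerbations are severe exacerbations (11.5.3.1) and so are events. A death recorded as discontinuation, for example for an adverse event, is also an event. The censoring sentence covers only subjects without the event, and similar wording is used for other time-to-event endpoints. Nor would all of an assumed 1-3% be censored: in the simulation, death came before any exacerbation or discontinuation in 0.67% of subjects at 1% mortality per year and 1.87% at 3%.

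The two claims also conflict for the same on-treatment death. If it is a premature discontinuation, J2R imputes but the composite counts an event. If it is not, the composite censors but the J2R text does not clearly reach the subject.

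**Conclusion.** The J2R rule is wrong for subjects who discontinue or withdraw and die before Week 52: both analyses credit them with exacerbations and person-time after death. At an assumed 1-3% mortality, mid-year on average, this is roughly 18-57 events and 20-60 person-years per 4,000-subject arm, and a rate-ratio shift of at most about 0.002 towards 1. The mortality and discontinuation rates are assumptions, and the calculation ignores covariates.

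It would be a mistake to infer that the primary result or type I error is at risk; neither is touched. The exacerbation-or-discontinuation analysis has an undefined term, not a demonstrated error. Severity: minor.

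**What to change.** In SAP 7.3.2.2, 7.3.2.3 and the J2R offsets in 11.5.3.1, end the unobserved period and the offset at min(projected Week 52 date, date of death). In the exacerbation-or-discontinuation definition in 11.5.3.1, state that an on-treatment death without an earlier event counts as premature treatment discontinuation on the date of death, in line with the completion definition in 11.5.1.3.

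The cost is a few lines of SAP text and trivial programming; dates of death are already used elsewhere in the plan. The downside is a slightly less conservative J2R estimate, by at most about 0.002 on the rate ratio under the assumptions above. Both changes should be made before Source Data Lock, by when the SAP synopsis requires analysis decisions to be settled.
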